**Nominal scale**

Item	Category	Remarks
AST/ALT $\leq$ 3-fold of institutional upper reference limit ( $\leq$ 5-fold of institutional upper reference limit if liver metastasis is observed)	Yes, No	
Chest CT normal	Yes, No	
Chest X-ray normal	Yes, No	
Measurement of markers for interstitial lung disease, such as KL-6, normal	Yes, No	
Pulmonary function test (PFT) normal	Yes, No	
Measurement of oxygen saturation normal	Yes, No	
Total cholesterol $\leq$ 350 mg/dL (9.9 mmol/L)	Yes, No	
Triglyceride $\leq$ 400 mg/dL (4.56 mmol/L)	Yes, No	
Hemoglobin A1C $<$ 10%	Yes, No	
Fasting blood glucose $\leq$ 1.5-fold of institutional upper reference limit	Yes, No	
Concomitant therapy (drug therapy)	Absent, Present	
Concomitant therapy (non-drug therapy)	Absent, Present	
History of smoking	Absent, Present	
Family history of diabetes mellitus	Absent, Present	
History of pulmonary surgery	Absent, Present	

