6.3 Concomitant therapy

6.3.1 Drug therapy

The following information will be recorded in each booklet of the case report form for all the drugs administered from the start date of the observation period to the date of safety evaluation. If an adverse event is noted, the drugs used during the period from the start day of the observation period to the onset of the adverse event and medications used for treatment of the adverse event should also be recorded.

- [1] Drug name (product name)
- [2] Administration route
- [3] Daily dosage
- [4] Daily dosing frequency
- [5] Administration period
- [6] Reason for the administration

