6.3.2 Non-drug therapy

The following information will be recorded in each booklet of the case report form for the non-drug therapy given from the start date of the observation period to the safety evaluation date. If an adverse event is noted, the non-drug therapy used during the period from the start day of the observation period to the onset of the adverse event and non-drug therapy used for treatment of the adverse event should also be recorded.

- [1] Name of therapy
- [2] Therapeutic period
- [3] Reason for the therapy

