### **8.2.5. Patient Demographics and Treatment History**

- Patient demographics**

The frequency tabulation of the following patient demographics and baseline characteristics will be performed in the safety analysis set and efficacy analysis set. Basic statistics will be tabulated for continuous scales.

For items using reference laboratory test values, results using corporate reference values will be tabulated separately from results using institutional reference values as necessary.

[Demographic and other baseline characteristics]:

- Sex [male, female];
- Age (continuous data);
- Age [ $<15$  years,  $\geq 15$  to  $<65$  years,  $\geq 65$  years];
- Age [ $<45$  years,  $\geq 45$  to  $<55$  years,  $\geq 55$  to  $<65$  years,  $\geq 65$  to  $<75$  years,  $\geq 75$  to  $<85$  years,  $\geq 85$  years];
- Age [ $<15$  years,  $\geq 15$  years];
- Age [ $<65$  years,  $\geq 65$  years];
- Body surface area ( $m^2$ ) [ $<1.2$ ,  $\geq 1.2$  to  $<1.4$ ,  $\geq 1.4$  to  $<1.6$ ,  $\geq 1.6$  to  $<1.8$ ,  $\geq 1.8$ ];
- Height (continuous data);
- Weight (continuous data);
- Body mass index (BMI) (continuous data);
- BMI [low weight ( $< 18.5$ ), ordinary weight ( $\geq 18.5$  to  $<25.0$ ), Obese Class I ( $\geq 25.0$  to  $<30.0$ ), Obese Class II ( $\geq 30.0$  to  $<35.0$ ), Obese Class III ( $\geq 35.0$  to  $<40.0$ ), Obese Class IV ( $\geq 40.0$ )];
- Inpatient/outpatient status [inpatient, outpatient];
- Past medical history [absent, present];

- Past history of lung disease [absent, present];
- Past history of interstitial lung disease [absent, present];
- Past history of hepatitis B, tuberculosis, and herpes zoster [absent, present];
- Past history of diabetes mellitus [absent, present];
- Complications [absent, present];
- Comorbid lung disease [absent, present];
- Comorbid interstitial lung disease [absent, present];
- Comorbid hepatitis B, tuberculosis, and herpes zoster [absent, present];
- Comorbid diabetes mellitus [absent, present];
- Hepatic dysfunction [absent, present];
- Severity of hepatic dysfunction [mild, moderate, severe];
- Renal dysfunction [absent, present];
- Severity of renal dysfunction [mild, moderate, severe];
- ECOG Performance Status [0, 1, 2, 3, 4];
- Karnofsky Performance Status [10-20, 30-40, 50-60, 70-80, 90-100];
- Risk classification (Memorial Sloan Kettering Cancer Center [MSKCC] Risk) [good (0 of 5 items), intermediate (1 to 2 of 5 items), poor (3 to 5 of 5 items)];

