The number of patients with CTCAE Grade  $\geq 3$  adverse reactions and the incidence of CTCAE Grade  $\geq 3$  adverse reactions will be tabulated by SOC and PT by category shown below. •Further tabulation of serious adverse reactions” will be followed for categories.

- Seriousness;
- Known/unknown;
- Outcome;
- Timing of initial onset;
- Intervention;
- Administration of this drug;
- Duration of treatment;
- Total dose.

- **Further tabulation of adverse events**

The number of patients with adverse events and the incidence of adverse events will be tabulated by SOC and PT by category shown below. “• Further tabulation of serious adverse reactions” will be followed for categories.

- CTCAE Grade.

- **Further tabulation of unknown adverse reactions**

The number of patients with unknown adverse reactions and the incidence of unknown adverse reactions will be tabulated by SOC and PT by category shown below. “•Further tabulation of serious adverse reactions” will be followed for categories.

- Outcome.

- **Cumulative incidence of adverse reactions**

The cumulative incidence of adverse reactions will be graphically presented with the time to onset on the horizontal axis.

The cumulative incidence will be graphically presented in the same manner for interstitial lung disease, diabetes mellitus/hyperglycemia, hypercholesterolemia/hyperlipidemia, infection, mucositis-related adverse events, and skin disorder among major investigation items.

- **Cumulative incidence of CTCAE Grade  $\geq 3$  adverse reactions**

The cumulative incidence of CTCAE Grade  $\geq 3$  adverse reactions will be graphically presented with the time to onset on the horizontal axis.

The cumulative incidence will be graphically presented in the same manner for interstitial lung disease, diabetes mellitus/hyperglycemia, hypercholesterolemia/hyperlipidemia, infection, mucositis-related adverse events, and skin disorder among major investigation items.

- **Incidence of adverse reactions by patient demographic**

The number of patients with adverse reactions and the incidence of adverse reactions will be tabulated by item listed in “[Section 10.1.1. Patient demographics to be used to evaluate safety and efficacy.](#)”

Fisher’s exact test will be performed for nominal scale data and Cochran-Armitage test (exact method) for ordered scale data.

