Tabulation will be performed in the same manner for interstitial lung disease, diabetes mellitus/hyperglycemia, hypercholesterolemia/hyperlipidemia, infection, mucositis-related adverse events, and skin disorder among major investigation items.

For items using reference laboratory test values, results using corporate reference values will be tabulated in addition to results using institutional reference values.

- **Incidence of CTCAE Grade  $\geq 3$  adverse reactions by patient demographic**

The number of patients with CTCAE Grade  $\geq 3$  adverse reactions and the incidence of CTCAE Grade  $\geq 3$  adverse reactions will be tabulated by item listed in “[Section 10.1.1. Patient demographics to be used to evaluate safety and efficacy.](#)”

Tabulation will be performed in the same manner for interstitial lung disease, diabetes mellitus/hyperglycemia, hypercholesterolemia/hyperlipidemia, infection, mucositis-related adverse events, and skin disorder among major investigation items.

For items using reference values, results using corporate reference values will be tabulated in addition to results using institutional reference values.

- **Incidence of adverse reactions by medical history, prior treatment history, and concomitant therapy**

The number of patients with adverse reactions and the incidence of adverse reactions will be tabulated by category shown below.

The number of patients and incidence will be tabulated in the same manner for interstitial lung disease among major investigation items.

- Past medical history;
- Complications;
- Prior medications.

- **Incidence of CTCAE Grade  $\geq 3$  adverse reactions by medical history, prior treatment history, and concomitant therapy**

The number of patients with CTCAE Grade  $\geq 3$  adverse reactions and the incidence of CTCAE Grade  $\geq 3$  adverse reactions will be tabulated by category shown below.

- Past medical history;
- Complications;

- Concomitant medications;
- Non-drug therapies;
- Prior medications.
- **Subgroups**

Safety in the following subgroups will be analyzed.

1. Children (<15 years), adults ( $\geq 15$  years).
2. Elderly ( $\geq 65$  years), non-elderly (<65 years).
3. Presence or absence of pregnancy.
4. Presence or absence of hepatic dysfunction.
5. Presence or absence of renal dysfunction.
6. By indication.
7. By whether criteria for proper use are met.
8. History of hepatitis B, tuberculosis, and herpes zoster.
9. Severity of hepatic dysfunction.
10. Sex.

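### The two concomitant-therapy flags are tested as baseline factors, but they are collected on treatment and can be switched to Present by treating the reaction itself

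*SAP*

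**What the plan says.** SAP 10.1.1 (nominal scale) contains "Concomitant therapy (drug therapy" and "Concomitant therapy (non-drug therapy", each categorised Absent/Present with an empty Remarks cell. Other on-treatment quantities in the same table (duration of treatment, total dose, dose intensity, relative dose intensity) are marked *No test*.

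SAP 8.2.6, adverse reactions by patient demographic, tabulates incidence by every 10.1.1 item and states that Fisher's "exact test will be performed for nominal scale data". It continues: "Tabulation will be performed in the same manner for interstitial lung disease", and names five further major investigation items. SAP 8.2.5 includes both flags in a list introduced as "the following patient demographics and baseline characteristics".

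The Protocol treats these variables differently. The observation schedule in section 6 has no start-of-administration entry for either type of concomitant therapy; both are recorded only across the three on-treatment intervals. Section 6.3.1 adds that "medications used for treatment of the adverse event should also be recorded", and section 6.3.2 adds that "non-drug therapy used for treatment of the adverse event should also be recorded".

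A separate SAP 8.2.6 table of Grade ≥3 reactions, by concomitant medication and by "Non-drug therapies", states no test.

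**The concern.** A factor that is to be read as influencing a reaction has to be fixed before the reaction can occur. Here a patient with no other therapy who has a reaction and is treated for it moves from Absent to Present because of the reaction. Patients without a reaction have no such route. Incidence is therefore pushed up among the Present and down among the Absent, even if other therapy has no bearing on risk. SAP 8.2.6 itself expects some interstitial lung disease (ILD) to be treated and some not, since it tabulates ILD by presence or absence of treatment.

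Examining influencing factors and ILD risk factors are Objectives 2 and 3, and the results are meant to inform proper use. A small p-value for either flag may mean only that the reaction was treated. The table and test would not let a reader separate that from a factor that came first.

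**Working it through.** **The plan's own figures.** These reproduce: 1 − 0.99^300 = 0.951 for at least one event at 1.0% incidence; P(X ≥ 40) = 0.968 for 300 cases at 17.1%; and 300/(1 − 0.5) = 600 registered. The concern does not depend on them. Only the target of 600 and the ILD planning incidence (14/82 = 17.1%, taken as 17%) are used below.

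**Inputs**
- N = 600 (Protocol 3); r = 0.17 (Protocol 3, ILD); two-sided 5% level (SAP 4).
- p0: share of patients Present for reasons unrelated to the reaction. Not in the documents; assumed.
- f: share of reactions for which the therapy is given. Not in the documents; assumed.

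**Model, with no true association**
- P(Present | no reaction) = p0
- P(Present | reaction) = 1 − (1 − p0)(1 − f)

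**Worked case: p0 = 0.10, f = 0.10**
- P(Present | reaction) = 1 − 0.90 × 0.90 = 0.19.
- Expected reactions: 600 × 0.17 = 102; no reaction: 498.
- Present: 102 × 0.19 = 19.4 with a reaction and 498 × 0.10 = 49.8 without. Incidence 19.4/69.2 = 28.0%.
- Absent: 82.6 with a reaction and 448.2 without. Incidence 82.6/530.8 = 15.6%.
- Odds ratio (0.19/0.81)/(0.10/0.90) = 2.11, where the true value is 1.

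**Share of simulated studies with Fisher p<0.05** (5,000 studies of 600 per setting)

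| Item | p0 | f | p<0.05 |
|---|---|---|---|
| Non-drug | 10% | 5% / 10% / 20% | 24.5% / 66.0% / 98.8% |
| Non-drug | 20% | 5% / 10% / 20% | 14.6% / 40.8% / 90.8% |
| Drug, premedication not counted | 60% / 80% / 90% | 30% | 61.1% / 26.5% / 11.0% |
| Drug, premedication not counted | 60% / 80% / 90% | 60% | 99.8% / 86.7% / 48.9% |
| Drug, premedication counted | 98% / 99% | 30% | 1.0% / 0.6% |
| Drug, premedication counted | 98% / 99% | 60% | 0.4% / 0.1% |
| Flag fixed at start of administration | 5% to 95% | 0 | 3.7% to 5.0% |

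A separate simulation at r = 17.1% and p0 = 20% (2,000 studies per setting) gave 40% and 91% for f = 10% and 20%, and 4.2% for f = 0. With 300 patients instead of 600, r = 17.1%, p0 = 10% and f = 10%, the rate is still 40%.

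The last row of the table is the control: once the reaction cannot alter the flag, the test keeps its level.

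**The case against.** **The flags' derivation is not shown.** Treatment of an event has its own field (Protocol 6.8, item [6]), and the SAP analyses intervention separately, so a programmer might keep event treatment out of the flags. That is possible, but neither document says so, and Protocol 6.3.1 and 6.3.2 place event treatment in the concomitant-therapy record. The default derivation therefore includes it.

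**The drug flag may be saturated.** The Protocol (section 2) describes an antihistamine before administration, and section 6.3.1 records all drugs. Read literally, almost everyone is Present and the reaction can hardly change that. This stands: the drug flag then fails by being uninformative, and the non-drug flag is the more exposed to bias.

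**The size rests on assumed inputs.** Other choices give less. With r = 17%, the rate is 5.5% at p0 = 20% and f = 2%, and 8% or 19% at p0 = 40% and f = 5% or 10%. At r = 5% and p0 = 20%, it is 7% or 17% for f = 5% or 10%; at r = 90%, 9% or 23%. The 99% figure is an upper corner. This stands as a limit on size, but any f above zero biases in the same direction. The effect is not confined to the ILD incidence: at r = 70%, p0 = 10% and f = 10%, the rate is 79%.

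**The test may not extend to ILD.** The Fisher sentence belongs to the table of all adverse reactions; for ILD the SAP says only that tabulation follows the same manner. Carrying the test over is the natural reading but is an inference. The tabulated incidences are distorted either way.

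**Impact is limited.** SAP 4 says the study is not confirmatory, these are two coarse flags among many, and therapies are also tabulated individually. This caps the severity. It does not make the comparison interpretable, because the individual tabulations in 8.2.5 do not relate therapy start to reaction onset.

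**Conclusion.** The concern holds. Two variables recorded after treatment starts, with therapy for the event included, are placed among baseline characteristics and tested as factors for adverse reactions. The direction of the bias is certain whenever any reaction is treated with a therapy that counts towards the flag.

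Its size is not known from the documents. In the settings simulated for the non-drug flag (10–20% background use, 5–20% of reactions treated, 17% incidence, 600 patients), a false association appears in about 15% to 99% of studies against a nominal 5%. Lower treatment shares, higher background use or other incidences bring this down, in some cases close to nominal. For the drug flag, the result runs from 11% to about 100% if premedication is left out, and to 1% or less if it is counted.

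The Grade ≥3 table shares the undefined exposure but states no test. The plan should be changed on this point. The harm is a misleading influencing factor in the safety results, not a wrong confirmatory conclusion.

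**What to change.** In SAP 10.1.1 and 8.2.6, define both flags as therapy ongoing at the start of administration, excluding infusion premedication and any therapy whose recorded reason is an adverse event. The reason filter is largely a safeguard, for example for therapy begun on Day 1 for a same-day reaction. The flags can be derived from the period and reason already collected (Protocol 6.3.1, items [5] and [6]; 6.3.2, items [2] and [3]). Use the same definition in the descriptive Grade ≥3 table.

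The alternative is to mark both items *No test*, as already done for dose and duration, and to present them descriptively with a note that they may include treatment of the reaction.

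A rule counting therapy started before onset should not be used. It shortens the exposure window only for patients with the reaction, and so creates a false protective signal.

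The cost is one definition line and a date-and-reason filter in programming, with no new data. What is given up is that therapy started during treatment is no longer assessed as a factor.

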### Nominal scale

Item	Category	Remarks
History of steroid use	Absent, Present	
History of occupational and environmental exposure to asbestos, pneumoconiosis-producing dusts, etc.	Absent, Present	
History of administration of highly concentrated oxygen for treatment of respiratory disease	Absent, Present	
Drug allergies	Absent, Present	
Allergies other than drug allergies	Absent, Present	
Dose at initiation	25 mg, others	
Duration of treatment (weeks)	>0 to ≤8 weeks, >8 to ≤16 weeks, >16 to ≤24 weeks, >24 to ≤48 weeks, >48 to ≤72 weeks, >72 to ≤96 weeks, >96 weeks	No test
Total dose (mg)	>0 to ≤200 mg, >200 to ≤400 mg, >400 to ≤600 mg, >600 to ≤1200 mg, >1200 to ≤1800 mg, >1800 to ≤2400 mg, >2400 mg	No test
Dose intensity (mg/week)	>0 to ≤10 mg, >10 to ≤15 mg, >15 to ≤20 mg, >20 to ≤25 mg, >25 to ≤30 mg, >30 mg	No test
Relative dose intensity	>0.0 to ≤0.4, >0.4 to ≤0.6, >0.6 to ≤0.8, >0.8 to ≤1.0, >1.0 to ≤1.2, >1.2	No test

### Ordered scale

Item	Category	Remarks
Age 1	<15 years, ≥15 to <65 years, ≥65 years	
Age 2	<45 years, ≥45 to <55 years, ≥55 to <65 years, ≥65 to <75 years, ≥75 to <85 years, ≥85 years	
Body surface area (m  )	<1.2, ≥1.2 to <1.4, ≥1.4 to <1.6 ≥1.6 to <1.8, ≥1.8	

### Ordered scale

Item	Category	Remarks
BMI	Low weight (<18.5), Ordinary weight ( $\geq 18.5$ to $<25.0$ ), Obese Class I ( $\geq 25.0$ to $<30.0$ ), Obese Class II ( $\geq 30.0$ to $<35.0$ ), Obese Class III ( $\geq 35.0$ to $< 40.0$ ), Obese Class IV ( $\geq 40.0$ )	
Severity of hepatic dysfunction	Mild, Moderate, Severe	
Severity of renal dysfunction	Mild, Moderate, Severe	
ECOG Performance Status	0, 1, 2, 3, 4	
Karnofsky Performance Status	10-20, 30-40, 50-60, 70-80, 90-100	
Risk classification (MSKCC Risk)	Good (0 of 5 items), Intermediate (1 to 2 of 5 items), Poor (3 to 5 of 5 items)	
Number of metastatic foci (at the initiation of treatment)	0, 1, $\geq 2$	
Disease stage (at the diagnosis of target disease)	STAGE0, STAGE1, STAGE2, STAGE3, STAGE4	
Duration of illness	$\geq 0$ to $\leq 12$ months, $\geq 13$ to $\leq 24$ months, $\geq 25$ to $\leq 48$ months, $\geq 49$ months
